### **8.2.3. Pregnancy Testing**

A urine pregnancy test for participants of childbearing potential will be performed at screening, before double-blind vaccination, before open-label vaccination, and before the booster vaccination. Participants of childbearing potential who originally received placebo and will not be receiving the Ad26.COV2.S vaccine under EUA do not need to complete a pregnancy test.

Additional serum or urine pregnancy tests may be performed for participants of childbearing potential, as determined necessary by the investigator or required by local regulation, to establish the absence of pregnancy at any time during the participation in the study.

### **8.2.4. Clinical Laboratory Assessments**

Blood samples for clinical laboratory assessments (as detailed in Section 10.2, Appendix 2) will be collected as described in the Schedules of Activities in Section 1.3.

In case of a thrombotic event or TTS, every effort should be made to collect local hospital/laboratory test results obtained by the treating physician to allow rapid diagnosis and

treatment. This information should be reported through the TTS AESI form (see Section 10.13, Appendix 13) electronically per instructions in the eCRF completion guidelines. In addition, every effort should be made to collect blood samples from the participant for a platelet count (local laboratory or substitute for local laboratory) and other applicable testing (central laboratory) (see the Schedule of Activities in Section 1.3.5 and Section 10.2, Appendix 2). The Investigator will review the laboratory test results to assist the investigation of the AESI.

See Section 8.3.7.1 for details on laboratory test details to be reported for an AE of thrombocytopenia.

### **8.3. Adverse Events, Serious Adverse Events, Medically-attended Adverse Events, Adverse Events of Special Interest, and Other Safety Reporting**

Timely, accurate, and complete reporting and analysis of safety information, including AEs, SAEs, suspected AESIs, MAAEs, and product quality complaints (PQCs), from clinical studies are crucial for the protection of participants, investigators, and the sponsor, and are mandated by regulatory agencies worldwide. The sponsor has established Standard Operating Procedures in conformity with regulatory requirements worldwide to ensure appropriate reporting of safety information; all clinical studies conducted by the sponsor or its affiliates will be conducted in accordance with those procedures.

AEs will be reported by the participant (or, when appropriate, by a caregiver or surrogate) during the reporting periods detailed below.

Further details on AEs, SAEs, suspected AESIs, MAAEs, and PQCs can be found in [Appendix 4](#).

#### **8.3.1. Time Period and Frequency for Collecting Adverse Event, Medically-attended Adverse Event, Adverse Events of Special Interest, and Serious Adverse Event Information**

##### **All Adverse Events**

For all participants (throughout the study regardless of any protocol amendment)a:

- (S)AEs that are related to study procedures or that are related to non-investigational sponsor products will be reported from the time a signed and dated ICF is obtained until the end of the study/early withdrawal.
- Clinically relevant medical events not meeting the above criteria and occurring between signing of the ICF and moment of vaccination in the double-blind phase of the study will be collected on the Medical History eCRF page as pre-existing conditions. This does not apply to the open-label phase.

a 90% of the participants who received a booster vaccination will be monitored for safety until 1 year post booster vaccination. The remaining 10% of the active participants who receive a booster vaccination will be monitored for safety at least for 6 months

- All SAEs and all AEs leading to study discontinuation (regardless of the causal relationship) are to be reported from the moment of vaccination until completion of the participant's last study-related procedure, which may include contact for safety follow-up. The sponsor will evaluate any safety information that is spontaneously reported by an investigator beyond the time frame specified in the protocol.
- MAAEs are defined as AEs with medically-attended visits including hospital, emergency room, urgent care clinic, or other visits to or from medical personnel for any reason. Routine study visits will not be considered medically-attended visits. New onset of chronic diseases will be collected as part of the MAAEs. MAAEs are to be reported for all participants from the moment of each vaccination until 6 months after the vaccination (applicable for both the double-blind and open-label phases of the study), except for MAAEs leading to study discontinuation which are to be reported during the entire study.
- Special reporting situations, whether serious or non-serious, will be recorded from the time of each vaccination until 28 days post-vaccination (applicable for both the double-blind and open-label phases of the study).
- All AEs will be followed until resolution or until clinically stable.

As of Amendment 7, for all participants:

- A passive follow-up approach is adopted, defined as follow-up by the site at Month 18 and Month 24 to document new COVID-19 participant-reported episodes as SAEs, AEs, or MAAEs. Participants may contact the site at any time in between scheduled visits to report COVID-19 episodes.
- Concomitant medications for these events should be reported.
- If a COVID-19 confirmatory laboratory or assay read-out is available, this should be reported in the eCRF (self-reported or as part of CIOMS form).
- Participants may contact the site at any time in between scheduled visits to report COVID-19 episodes.
- Events ongoing at time of informed consent do not need to be reported as AEs, SAE, or MAAEs, only new onset of COVID-19 events need to be reported.
- 90% of the participants who received a booster vaccination will be monitored for safety until 1 year post booster vaccination. The remaining 10% of the active participants who receive a booster vaccination will be monitored for safety at least for 6 months.

For participants in the Safety Subset (double-blind phase):

- Solicited AEs, collected through an e-Diary, will be recorded from the time of vaccination until 7 days post-vaccination.
- All other unsolicited AEs, whether serious or non-serious, will be recorded from the time of vaccination until 28 days post-vaccination.

Up to Amendment 7: For all participants who received booster vaccination at the Year 1/Booster Visit:

- Solicited AEs, collected through an e-Diary, will be recorded from the time of vaccination until 7 days post-vaccination. All participants will collect signs and symptoms in the e-Diary, if feasible. For a subset of participants, ie, participants included in the Safety Subset of the double-blind study phase and all participants who received a heterologous COVID-19 vaccination outside the study, the e-Diary will be reviewed by the study personnel and solicited AEs recorded in the eCRF, if feasible. All other unsolicited AEs, whether serious or non-serious, will be recorded from the time of vaccination until 28 days post-vaccination for all participants who received the booster at Year 1/Booster Visit.

As of Amendment 7, solicited and unsolicited AE reporting will stop for all participants.

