## 8. STUDY ASSESSMENTS AND PROCEDURES

### Overview

The [Schedules of Activities](#) summarize the frequency and timing of all measurements applicable to this study.

Up to Amendment 7, all participants will be provided access to an eCOA digital tool. This eCOA will be used to collect COVID-19 signs and symptoms surveillance info for all participants, ePRO (Symptoms of infection with Coronavirus-19 [SIC], including body temperature, and pulse oximetry results) for all participants at baseline and in case of COVID-19-like signs and symptoms, and e-Diary data on 7-day reactogenicity (solicited signs and symptoms, including body temperature) in the Safety Subset and all participants who receive booster vaccination at the Year 1/Booster Visit, if feasible. All eCOA assessments should be conducted/completed before any tests, procedures, or other consultations to prevent influencing participant responses. Refer to the PRO completion guidelines for instructions on the administration of ePROs.

As of Amendment 7, the number of on-site visits for participants who are not part of the Immunogenicity or Booster Subsets is reduced. For these participants, any outstanding Visits 8 and 9 are cancelled. In addition, any outstanding Visits 10 and 11 are replaced by a phone call. No further booster vaccination will be provided in the protocol. In addition, requirements for COVID-19 episodes reporting are changed (ie, a passive follow-up approach is adopted, defined as safety follow-up by the site at Month 18 and Month 24 to document COVID-19 participant-reported events as SAE, AE, or MAAE until end of study). All participants will be reconsented at an unscheduled visit and as per local informed consent process guidelines.

If multiple assessments are scheduled for the same timepoint, it is recommended that procedures be performed in the following sequence: vital signs before blood draws. If needed, assessments may be performed on another day within the applicable visit window. Actual dates and times of assessments will be recorded in the source document, the eCRF, or the sample requisition form.

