### **8.1.2. Procedures in the Event of (Suspected) COVID-19**

#### **8.1.2.1. Passive Follow-up (As of Amendment 7)**

As of Amendment 7, active follow-up of suspected COVID-19 episodes will be replaced by a passive follow-up approach. For COVID-19 events that are ongoing at the time of informed consent:

[figure not shown]
- a. Participant will be instructed to stop using the eCOA.
- b. Any outstanding activities planned for the follow-up of COVID-19 events will end as of the consent.
- c. No further sampling for participants and no Day 1-2, Day 3-4, and Day 29 visit will be performed
- d. MRU and MA-COV forms are no longer to be completed

The eCOA will be stopped based on approval of protocol Amendment 7 at each study site. From that point onwards, active participants are no longer able to use eCOA.

For new suspected COVID-19 episodes no samples will be collected in the context of the study. Site staff will collect information on new COVID-19 episodes at scheduled time points and report these as SAEs, AEs, or MAAEs, as applicable. Participants may contact the site at any time in between scheduled visits to report COVID-19 episodes. Concomitant medications for each COVID-19 episode are to be reported into the eCRF as well as any laboratory confirmation of COVID-19, if available.

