### **8.3.6. Disease-related Events and Disease-related Outcomes Not Qualifying as Adverse Events or Serious Adverse Events**

(S)AEs caused by molecularly confirmed SARS-CoV-2 infection will be removed at the analysis level from the (S)AE listings and tables and presented separately.

All events that meet the definition of an SAE will be reported as SAEs, regardless of whether they are protocol-specific assessments.

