#### **Serious Adverse Event**

An SAE based on ICH and EU Guidelines on Pharmacovigilance for Medicinal Products for Human Use is any untoward medical occurrence that at any dose:

- Results in death
- Is life-threatening  
(The participant was at risk of death at the time of the event. It does not refer to an event that hypothetically might have caused death if it were more severe)
- Requires inpatient hospitalization or prolongation of existing hospitalization
- Results in persistent or significant disability/incapacity
- Is a congenital anomaly/birth defect
- Is a suspected transmission of any infectious agent via a medicinal product

- Is Medically Important\*

\*Medical and scientific judgement should be exercised in deciding whether expedited reporting is also appropriate in other situations, such as important medical events that may not be immediately life-threatening or result in death or hospitalization but may jeopardize the participant or may require intervention to prevent 1 of the other outcomes listed in the definition above. These should usually be considered serious.

If a serious and unexpected AE occurs for which there is evidence suggesting a causal relationship between the study vaccine and the event (eg, death from anaphylaxis), the event must be reported as a SUSAR even if it is a component of the study endpoint (eg, all-cause mortality).

Any respiratory tract infection fulfilling the criteria of an SAE will be reported as such during the entire study. If the molecular test is positive for SARS-CoV-2, the SAE will be excluded from the SAE analysis in the Clinical Study Report, and will be tabulated separately.

As of Amendment 7, a passive follow-up approach is adopted: the investigator will place a phone call at Month 18 and Month 24 to collect information on any protocol required safety information (see Section 8.3.1). In addition, SAEs, AEs, and MAAEs related to COVID-19 need to be reported together with the concomitant medications related to these events until study end. Any confirmatory COVID-19 laboratory finding should be reported in the eCRF.

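### Amendment 7's exemption of COVID-19 events ongoing at reconsent from SAE reporting contradicts the protocol's own all-SAE rules, so later serious worsening of such an episode may go unreported

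*Protocol*

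**What the plan says.** Amendment 7 replaces active COVID-19 surveillance with passive follow-up. Under the Section 8 Overview, "All participants will be reconsented at an unscheduled visit and as per local informed consent process guidelines". Two instructions take effect at that reconsent:

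- **Reporting (Section 8.3.1, Amendment 7 list):** "Events ongoing at time of informed consent do not need to be reported as AEs, SAE, or MAAEs"; only COVID-19 of new onset is to be reported. The same list defines passive follow-up as site contact at Month 18 and Month 24 "to document new COVID-19 participant-reported episodes as SAEs, AEs, or MAAEs".
- **Follow-up (Section 8.1.2.1, ongoing COVID-19 events):** "Any outstanding activities planned for the follow-up of COVID-19 events will end as of the consent". The eCOA, sampling and COVID-19 visits stop, and "MRU and MA-COV forms are no longer to be completed".

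Other sections say the opposite about serious events. Section 8.3.6 states: "All events that meet the definition of an SAE will be reported as SAEs, regardless of whether they are protocol-specific assessments". Section 10.4.1 states: "Any respiratory tract infection fulfilling the criteria of an SAE will be reported as such during the entire study". The general list in Section 8.3.1, whose header says it holds whatever the amendment, requires every SAE to be reported from vaccination to the last study procedure.

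**The concern.** The protocol gives sites two incompatible instructions about the same event. A participant with mild COVID-19 at reconsent who is admitted to hospital a week later has an SAE under the general rules. Under the Amendment 7 list, the episode was ongoing at consent and need not be reported as one. The COVID-19 procedures that would otherwise have recorded the admission ended at the same consent.

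Two things are at stake. The first is completeness of serious-event reporting, which Section 8.3 itself describes as crucial for participant protection. The second is severity classification. After Amendment 7 the Clinical Severity Adjudication Committee works from passive follow-up material: Section 8.1.3.4 gives hospitalisations reported as SAEs as its example, and Section 8.1.3.6 lists AE/SAE data, CIOMS forms and local laboratory results. An admission that a site leaves unreported may not reach the committee. If sites resolve the conflict differently, serious outcomes will be recorded unevenly across sites in the open-label and booster data.

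**Working it through.** No arithmetic applies. The check sets the rules side by side and then follows cases through them.

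**Rules that exempt or narrow**

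| Place | Effect |
|---|---|
| 8.3.1, Amendment 7 list | Events ongoing at consent need not be reported as AE, SAE or MAAE; only new-onset COVID-19 is reported |
| 8.1.2.1 | Outstanding COVID-19 follow-up, sampling, visits and the MRU and MA-COV forms end at consent; sites collect information on new episodes |
| 8.3.1, Serious Adverse Events | The monthly SAE reminder is replaced by passive follow-up |

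**Rules that require reporting**

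| Place | Effect |
|---|---|
| 8.3.1, general list | All SAEs, vaccination to last study procedure, whatever the amendment; AEs followed until resolved or stable |
| 8.3.1, Serious Adverse Events | All SAEs during the study go to the sponsor within 24 hours of site knowledge |
| 8.3.6 | No disease-related exemption at the reporting level |
| 10.4.1, Serious Adverse Event | Respiratory infections meeting SAE criteria are reported for the whole study |
| 10.4.5, Serious Adverse Events | Events requiring hospitalisation are SAEs; the listed exceptions do not include ongoing COVID-19; cause of death is an SAE |
| 9.2.4.2 and 10.4.1, Amendment 7 text | COVID-19-related SAEs, AEs and MAAEs are reported until study end, with no limit to new onset |

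The last row matters because the conflict is not simply newer text overriding older text. Amendment 7 contradicts itself.

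**Cases**

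1. *Episode begins after reconsent.* Both sets of rules require reporting. No conflict.
2. *Episode already serious before reconsent.* It was reportable as an SAE before the exemption applied, and Section 10.4.5 requires an unresolved SAE to be followed at end of study or discontinuation. Little is lost.
3. *Episode non-serious at reconsent, participant later dies.* Section 10.4.5 makes the cause of death an SAE, and Section 7.2 has death recorded in the eCRF as the reason for withdrawal. The fact of death is kept; whether an SAE report accompanies it depends on the rule the site follows.
4. *Episode non-serious at reconsent, participant later hospitalised or otherwise meets an SAE criterion.* The general rules require an SAE report and the Amendment 7 list waives it. No COVID-19-specific form remains. This is where the contradiction has practical effect.

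**Size.** The number of case 4 events would need the number of episodes open at reconsent and the chance that such an episode becomes serious afterwards. The document gives neither.

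**The case against.** The best defence is that the exemption is transitional. As of Amendment 7, Section 10.4.1 has COVID-19 reported as an SAE, AE or MAAE, and the bullet sits in the list introducing that change. It may only be meant to spare sites from re-entering episodes already recorded under the active procedures. That is plausible, and it disposes of case 2. It does not cover case 4, because the worsening happens after those procedures have stopped and so has not been recorded anywhere.

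A second defence is that the general SAE rules still stand, and that Sections 9.2.4.2 and 10.4.1 have the Month 18 and Month 24 calls collect any required safety information, not only new episodes. The Section 8 Overview also describes passive follow-up without restricting it to new episodes. This stands as a limit on the claim. A reader might infer that a hospitalisation or death in an ongoing case is recorded nowhere and that the adjudication committee could never learn of it. The documents do not support that. A site following the general rules would report the event on the SAE form, deaths have their own route, and Section 8.1.3.6 allows adjudication on all available relevant information and readjudication when more arrives. What remains is that the specific instruction, in the section sites use to decide what to report, tells them they need not.

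A reader might also try to put a number on the loss by combining an assumed share of open episodes with the planned enrolment of about 40,000 and the 2.5% case-hospitalisation ratio in Section 9.2.1. That is not supportable. The share has no source in the document, planned enrolment is not the number still active at Amendment 7, and the ratio is a planning value for the whole course of a case, including admissions before reconsent.

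Finally, Section 9.8 has open-label and booster endpoints summarised descriptively, so no confirmatory result is shown to be affected. That is correct.

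**Conclusion.** The point holds as an internal inconsistency. The exemption in Section 8.3.1, together with the end of follow-up in Section 8.1.2.1, conflicts with the all-SAE, hospitalisation and respiratory-infection rules and with Amendment 7's own text on COVID-19-related SAEs. An episode that is non-serious at reconsent and serious later may go unreported as an SAE and may be missed by severity adjudication, depending on which rule a site applies. The number affected cannot be derived.

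It should be corrected whatever that number is, because a protocol cannot tell sites both that every SAE is reported and that some need not be. The conclusion assumes that the consent meant is the Amendment 7 reconsent, which the context supports. It also assumes that nothing in the parts not at hand (the Schedules of Activities, and figures missing around the safety-reporting overview and Section 8.1.2.1) limits the exemption. Even if something there did, the sentence in Section 8.3.1 would still need to agree with it.

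**What to change.** Reconcile the sections by amending the bullet in Section 8.3.1:

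- Limit the exemption to ongoing COVID-19 episodes that are non-serious.
- Add a sentence such as: *An ongoing COVID-19 episode that meets, or later meets, an SAE criterion is reported as an SAE under the general rules, with its outcome and date.*
- Add a cross-reference in Section 8.1.2.1 so that ending the COVID-19 procedures is not read as ending SAE reporting.
- At the planned Month 18 or Month 24 contact, ask for the outcome of any episode that was open at reconsent. This makes explicit what Sections 9.2.4.2 and 10.4.1 already imply.

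The cost is a sentence or two of protocol text, a site memo and whatever extra SAE forms result. No visit, sample or treatment rule changes.

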### **Adverse Events of Special Interest**

Suspected AESIs (thrombotic events and thrombocytopenia [defined as platelet count below 150,000/ $\mu$ L]) will be recorded from the moment of vaccination until the end of the study/early withdrawal (see Section 8.3.7). An AESI Adjudication Committee with appropriate expertise will be established to evaluate each suspected AESI and determine whether it is a case of TTS. From the time of local approval of protocol Amendment 5 onwards, TTS is considered an AESI.

### **Serious Adverse Events**

All SAEs, as well as PQCs, occurring during the study must be reported to the appropriate sponsor contact person by study-site personnel within 24 hours of their knowledge of the event.

[figure not shown]
SAEs, including those spontaneously reported to the investigator before the end of the study, must be reported using an SAE form. The sponsor will evaluate any safety information that is spontaneously reported by an investigator beyond the time frame specified in the protocol.

Up to Amendment 7, participants will be reminded once a month to contact the study site in case of an SAE. As from Protocol Amendment 7, this is replaced by the passive follow-up approach.

All study participants will be monitored for SAEs for up to 2 years after their double-blind vaccination.

Information regarding SAEs will be transmitted to the sponsor using the SAE Form and Safety Report Form of the eCRF, which must be completed and reviewed by a physician from the study site and transmitted to the sponsor within 24 hours. The initial and follow-up reports of an SAE should be transmitted electronically or by facsimile (fax). Telephone reporting should be the exception and the reporter should be asked to complete the appropriate form(s) first.

